#### 7.5.5.3.2 Type of bleeding episode

When a bleeding episode or hemorrhage is reported, it will be classified as 1 of 2 types: spontaneous or traumatic.

##### Spontaneous bleeding episodes

Bleeding episodes should be classified as spontaneous if a patient/caregiver records a bleeding event when there is no known contributing factor such as a definite trauma or antecedent “strenuous” activity. The determination of “strenuous” is at the discretion of the investigator, and the patient/caregiver needs to be instructed by the investigator.

##### Traumatic bleeding episodes

Bleeding episodes should be classified as traumatic if the patient/caregiver records a bleeding episode even when there is a known or believed reason for the bleed. For example, if a patient were to exercise strenuously and then have a bleeding episode in the absence of any obvious injury, the bleeding episode would still be recorded as traumatic. Target joint bleeding episodes can be traumatic if a known action led to bleeding into the joint. The investigator should consider whether events resulting in a traumatic bleeding episode qualify as AEs i.e. is clinically significant, and should be reported as such. If hospitalization is required, an SAE should be reported.

#### 7.5.5.3.3 Data to be captured

In the event of a bleeding episode, the following information should be collected in the diary or CRF:

- The type of bleeding episode (that is, spontaneous or traumatic) and if related to sports activity or physical activity
- The date the bleeding event occurred
- The product (rFVIIa, aPCCs, rFVIIIFc [include specific drug name], etc.) and dose administered to treat the bleeding episode including any repeat doses
- The location of the bleed

The patient diary will serve as the source document for bleeding episodes between visits. Bleeding episodes during study visits will be recorded in the CRF.

The clinical sites and Clinical Monitors will ensure that there is consistency between the patient’s medical record, dispensing records, source documents, diary, and CRFs. During the study visits the investigator will verify whether or not a bleeding episode has occurred and was “spontaneous” or “traumatic.” The patient/caregiver will also be reminded about timely diary completion.

Bleeding episodes will not be reported as AEs unless they fulfill the criteria for an SAE; however, the concomitant events associated with a bleeding episode should be reported as AEs as appropriate (e.g., a fracture in an elbow).

## 7.5.6 Safety assessments

### 7.5.6.1 Adverse events

#### 7.5.6.1.1 Definitions

##### **Adverse event**

An Adverse event (AE) is any untoward medical occurrence in a patient administered a pharmaceutical product and that does not necessarily have a causal relationship with this treatment. An AE can therefore be any unfavorable and unintended sign (including abnormal laboratory finding), symptom, or disease temporally associated with the use of a medicinal (investigational) product, whether or not related to the medicinal (investigational) product.

Bleeding episodes in this patient population are not considered AEs. Bleeding episodes that meet a serious criterion should be reported as an SAE. All bleeding episodes that occur outside the study visit will be captured in the diary that the patient or the patient's caregivers will be maintaining throughout the study period.

Adverse events include the following:

- Abnormal test findings, as specified below.
- Clinically significant signs and symptoms.
- Changes in physical examination findings, i.e. worsening from baseline
- Progression/worsening of underlying disease.

In addition, signs and symptoms resulting from the following should also be handled according to the same principles as Adverse Events:

- Overdose
- Withdrawal of treatment
- Interactions
- Abuse
- Misuse

##### **Overdose**

An overdose is any dose of study treatment given to a subject or taken by a subject that exceeds the dose described in the protocol. Overdoses are not considered AEs; however if an overdose results in an AE, the AE must be recorded. Dosing information is to be recorded on the CRF.

## Abnormal test findings

An abnormal test finding, e.g. abnormal laboratory analysis results, vital signs or ECG, should be recorded as an Adverse Event in any of the following situations:

- The test is associated with accompanying symptoms. Note, that the symptom, not the test result, should be recorded as an AE.
- The test result leads to a medical/surgical intervention (the medical condition for which the procedure was performed should be reported record), including withdrawal of rFVIIIFc or discontinuation from the study. Repeat/confirmatory testing is not considered a medical intervention.
- The investigator considers the test result to be clinically significant.

## Preexisting conditions

A preexisting condition (i.e., a disorder present before the adverse event reporting period started and noted on the pretreatment medical history/physical examination form) should not be reported as an adverse event unless the condition worsens or episodes increase in frequency during the adverse event reporting period.

## Procedures

Diagnostic and therapeutic non-invasive and invasive procedures, such as surgery, should not be reported as adverse events. However, the medical condition for which the procedure was performed should be reported if it meets the definition of an adverse event. For example, an acute appendicitis that begins during the adverse event reporting period should be reported as the adverse event and the resulting appendectomy entered in the comments section of the CRF.

## Lack of efficacy

If there is a relapse of inhibitor after initial successful ITI this will be captured as an SAE, “relapse of inhibitor” and not as “lack of efficacy”.

## Serious adverse event (SAE)

An adverse event that meets one or more of the following criteria/outcomes is classified as serious:

- Results in death.
- Is life-threatening (i.e., at immediate risk of death).
- Requires in-patient hospitalization or prolongation of existing hospitalization.
- Results in persistent or significant disability/incapacity.
- Is a congenital anomaly/birth defect (i.e., in an offspring to the study patient).

Other medically important adverse events that may not result in death, be life threatening, or require hospitalization may be considered serious when, based upon appropriate medical

judgment, they may jeopardize the patient or may require medical or surgical intervention to prevent one of the outcomes listed above. Examples of such events are intensive treatment in an emergency room or at home for allergic bronchospasm, blood dyscrasias or convulsions that do not result in hospitalization or development of dependency or abuse.

In this study, the following events are considered medically important and must be reported as SAEs:

- Development of a confirmed positive inhibitor (>0.6 BU) during the tapering or follow-up periods
- A patient develops a Grade 2 or greater allergic reaction in association with administration of rFVIIIFc defined as follows using the Recommendations for Grading of Acute and Subacute Toxic Effects on the WHO scale [[WHO Handbook 1979](#)] [40]:
  - Grade 2: bronchospasm; no parenteral therapy needed
  - Grade 3: bronchospasm; parenteral therapy required
  - Grade 4: anaphylaxis

Allergic reactions, including anaphylaxis, have been reported with FVIII products. The patients/caregivers should be informed of early symptoms and signs of hypersensitivity reactions, including difficulty breathing, chest tightness, swelling of the face, rash, or hives. If such an event occurs while the subject is at home, the patients/caregivers should be instructed to seek immediate medical care for the subject.

- A patient develops a vascular thrombotic event, with the exception of IV injection site thrombophlebitis

The patient and/or the patient's legally authorized representatives will be informed of the early symptoms and signs of thrombotic phenomena, including pain and/or tenderness along a vein, unexpected swelling of an arm or leg without pain or tenderness, redness along a vein, low fever without any known reason (such as a cold or flu), sudden shortness of breath or difficulty breathing, or coughing, sudden chest pain, sudden severe headache or changes in vision, and numbness or tingling in arms or legs. If such an event occurs while the patient is at home, the patient and/or the patient's caregivers will be instructed to seek immediate medical care for the patient.

Serious also includes any other event that the investigator or company judges to be serious. Any suspected transmission of an infectious agent via rFVIIIFc shall also be considered serious.

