#### **6.1.1 Primary endpoint**

ITI success, defined as achieving all 3 of the following criteria:

- Negative titer for inhibitor (<0.6 BU/mL by the Nijmegen-modified Bethesda assay) at 2 consecutive visits
- FVIII incremental recovery (IR) >66% of the expected IR at 2 consecutive visits.
- FVIII elimination half-life ( $t_{1/2}$ )  $\geq$  7 hours

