#### Relapse

Relapse is defined as the occurrence of the following (with or without clinical signs or symptoms) after complete ITI success, based on the International ITI criteria [15]:

- A positive inhibitor ( $\geq 0.6$  BU using the Nijmegen assay) on 2 consecutive assessments, performed within 2-4 weeks

AND

- An IR  $\leq 66\%$  of the expected IR , on 2 consecutive assessments, performed within 2-4 weeks

If any assessments indicate relapse at any time during tapering or follow-up, the tests must be repeated at an unscheduled visit within 2 to 4 weeks to confirm relapse. A patient with confirmed relapse criteria will complete the end of treatment visit.

Throughout the tapering period all rFVIIIFc administration and any bleeding episodes will be registered by the patient and/or his caregiver in a study specific diary. The diary data will be reviewed by the investigator on an ongoing basis and discussed with the patient at each visit.

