**6.1.5.4 Relapse**

Relapse in the tapering or follow-up period is defined as the occurrence of any of the following (with or without clinical symptoms) after complete ITI success:

1. Positive inhibitor ( $\geq 0.6$  BU/mL), on two consecutive assessments performed within 2-4 weeks  
 AND  
 2. An  $IR \leq 66\%$  of the expected IR, on two consecutive assessments performed within 2-4 weeks

For relapse the date at which relapse criteria was met will be recorded.

The time in days between relapse and ITI success will be derived, as the difference between the two dates.

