#### **6.3.12.2 FVIII:C Levels**

For the FVIII:C the following listings will be produced:

- All local laboratory FVIII:C measurements, including period, visit, assay used, date, nominal and actual time, purpose of sample and result (absolute value for all samples).
- All determinations of incremental recoveries, based on results from local laboratory including period, visit, date, observed and expected IR (incl. units), and ratio of observed to expected IR (as percentage) (see Section 6.1.5.2.2 for derivation). Determinations that indicate either confirmed IR  $\geq 66\%$  of the expected IR, ITI success (complete or partial) or relapse will be flagged for the recorded observed/expected percentage. The listing will also contain whether the investigator considered the IR to be  $\geq 66\%$  and flags where this contradicts the derived ratio.

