**Treatment Outcome**

Table 14.2.1.1	Analysis of ITI Outcome (ITIFAS)
Table 14.2.1.2	Analysis of Prognostic Factors for ITI Outcome (ITIFAS)
Table 14.2.1.3	Descriptive Analysis of Time to ITI Success Criteria Met (ITIFAS)
Table 14.2.1.4	Kaplan-Meier Analysis of Time to ITI Success (ITIFAS)
Table 14.2.1.5	Kaplan-Meier Analysis of Time to Confirmed Negative Titer (ITIFAS)
Table 14.2.1.6	Kaplan-Meier Analysis of Time to Confirmed Incremental Recovery Greater Than Two Thirds of the Expected and Time to Confirmed Half-life >7 hours (ITIFAS)
Table 14.2.1.7	Summary of Relapse (TPFAS)
Table 14.2.1.8	Descriptive Analysis of Time to Relapse (TPFAS)

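### The SAE item for a confirmed positive inhibitor (>0.6 BU) omits exactly 0.6 BU, which both documents define as positive; a few SAP output labels need similar boundary corrections

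*Protocol*

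**What the plan says.** **Inhibitor titer.** Success criterion 1 (Protocol 6.1.1) is "Negative titer for inhibitor (<0.6 BU/mL by the Nijmegen-modified Bethesda assay) at 2 consecutive visits". Relapse (Protocol 7.1.3) requires "A positive inhibitor ( $\geq 0.6$ BU using the Nijmegen assay) on 2 consecutive assessments". Treatment failure (Protocol 7.1.2, SAP 6.1.5.3) and relapse in SAP 6.1.5.4 also place positive at ≥0.6. The study-specific SAE item, worded identically in Protocol 7.5.6.1.1 and SAP 6.1.6.1, is "Development of a confirmed positive inhibitor (>0.6 BU) during the tapering or follow-up periods".

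**Relapse as an SAE.** Protocol 7.5.6.1.1, under Lack of efficacy, states: "If there is a relapse of inhibitor after initial successful ITI this will be captured as an SAE". SAP 6.1.6.1 says the same in substance. Relapse has two elements joined by AND: a positive inhibitor, and IR at or below 66% of expected. Each must be shown "on two consecutive assessments performed within 2-4 weeks" (SAP 6.1.5.4).

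**Incremental recovery.** Criterion 2 is "FVIII incremental recovery (IR) >66% of the expected IR at 2 consecutive visits". The item recorded from the investigator (SAP 6.1.5.2.2) is also >66%. The IR listing in SAP 6.3.12.2 flags confirmed IR at ≥66%, describes the investigator's answer as ≥66%, "and flags where this contradicts the derived ratio".

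**Half-life.** Criterion 3 is ≥7 hours in both documents, with no requirement for a second determination. SAP section 8 titles Table 14.2.1.6 "Kaplan-Meier Analysis of Time to Confirmed Incremental Recovery Greater Than Two Thirds of the Expected and Time to Confirmed Half-life >7 hours". The half-life listing in SAP 6.3.12.2 keeps ≥7 hours but also speaks of a confirmed half-life.

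**The concern.** The SAE item uses the term for a confirmed positive inhibitor but attaches a different boundary from the one that defines positive. A site following the item as written would not have to report a confirmed 0.6 BU. This is one of the few events the protocol singles out for mandatory serious reporting, and reappearance of the inhibitor is the main thing tapering and follow-up are monitored for. Low titers are plausible: the protocol's own background (5.1.2) cites a relapse at 0.8 BU and a titer of 0.7 BU/mL on treatment, although both lie above either cut-off.

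The SAP slips matter less. A consistency check in a listing could flag a correct investigator answer as an error, and a secondary table could apply a slightly different rule from the criterion it describes.

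**Working it through.** The plan gives no figure to reproduce. The check sets each wording side by side and classifies values on and around each boundary.

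**Step 1. Titer.** Cut-offs are from Protocol 6.1.1 (negative), Protocol 7.1.3 and SAP 6.1.5.4 (positive), and Protocol 7.5.6.1.1 and SAP 6.1.6.1 (SAE item).

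| Confirmed titer (BU/mL) | Negative, <0.6 | Positive, ≥0.6 | Listed SAE, >0.6 |
|---|---|---|---|
| 0.5 | yes | no | no |
| 0.59 | yes | no | no |
| 0.6 | no | yes | **no** |
| 0.61 | no | yes | yes |
| 0.7 | no | yes | yes |

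Only 0.6 is affected. If laboratories report to one decimal (an assumption; the documents do not say), it is the lowest positive result.

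**Step 2. Does another route capture a confirmed 0.6?**

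- IR ≤66% on two assessments: both relapse elements are met, so it is an SAE through relapse.
- IR still >66%: relapse is not met and the listed item is not met. What remains is the general clause on events that the investigator or company considers serious, which is a judgement and not a rule.

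**Step 3. IR, as a percentage of expected.**

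| IR (%) | Success, >66 | Relapse limit, ≤66 | Listing, ≥66 | Table title, >two thirds |
|---|---|---|---|---|
| 65.9 | no | yes | no | no |
| 66.0 | no | yes | **yes** | no |
| 66.1 | yes | no | yes | **no** |
| 66.6 | yes | no | yes | **no** |
| 66.7 | yes | no | yes | yes |

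The listing differs from the criterion only at exactly 66%. If the same ≥66% is applied to the derived ratio, an investigator who correctly answers no to >66% at that value would be flagged as contradicting it.

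The title moves the bar by 66.67 − 66 = 0.67 percentage points. The documents give no value for expected IR. For assumed values in IU/dL per IU/kg:

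- 1.5: 0.66 × 1.5 = 0.99 against 2/3 × 1.5 = 1.00
- 2.0: 1.32 against 1.33
- 2.5: 1.65 against 1.67

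In each case one two-decimal IR (1.00, 1.33 or 1.66) passes >66% and fails the title's rule.

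**Step 4. Half-life.** 6.9 h fails both ≥7 and >7, and 7.1 h passes both. 7.0 h passes the criterion and fails the title.

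**Step 5. Which text governs Table 14.2.1.6?** SAP 6.3.13.1 gives >66% for the IR analysis, as does the title of companion Figure 14.2.1.3. For half-life it provides only a descriptive time to meeting the criterion. Its list of additional Kaplan-Meier analyses names negative titer and IR, so the table title is the only place that names a Kaplan-Meier analysis of half-life.

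**The case against.** The best defence is that nothing operative is inconsistent. Success, partial success, failure and relapse use matching boundaries across both documents, and >66% for success with ≤66% for relapse are proper complements. The local-versus-central laboratory tables use the same cut-offs. All of this stands.

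On the SAE item, one can argue that relapse is already serious and that the general clause catches the rest. The first part covers only patients whose IR has also fallen. The second makes reporting discretionary for an event the protocol meant to make mandatory. Two looser readings would close the gap: taking relapse of inhibitor under Lack of efficacy to mean any reappearance, or taking the SAP's lead-in to its relapse definition, which speaks of any of the elements, as making one sufficient. Neither fits the AND that joins the two elements in both documents.

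On the SAP slips, the listing prints observed IR, expected IR and their ratio, so a reader can see an exact 66%. The SAP also does not separately state the cut-off applied to the derived ratio. A title in an output list does not normally override the method text. These points stand and make the slips housekeeping. The exception is the half-life Kaplan-Meier analysis, which has no method text of its own to fall back on.

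**Conclusion.** The SAE threshold should be corrected: as written, it excludes a value that both documents define as positive. The uncovered case is a confirmed titer of exactly 0.6 BU with IR still >66%, in a patient who has reached ITI success. The documents give no basis for predicting how often this will occur. Only successes among the 20 planned patients are at risk of it, so it should be rare.

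The other effects are confined to listing flags at an IR of exactly 66%, and to one secondary Kaplan-Meier table if it is programmed from its title.

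A reader might infer that patients near a boundary will be misclassified in the primary result, where one of 20 patients is 1/20 = 5 percentage points. The documents do not support that. The definitions that generate ITI outcome and relapse agree, so the primary success and relapse proportions do not change if those definitions are programmed.

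**What to change.** 1. Protocol 7.5.6.1.1 and SAP 6.1.6.1: state the confirmed positive inhibitor in the SAE item as ≥0.6 BU/mL, the documents' own definition.
2. SAP 6.3.12.2, IR listing: use >66%, compared on the unrounded ratio, both for the flag and for the check against the investigator's answer.
3. SAP section 8, Table 14.2.1.6: retitle to IR >66% of expected and half-life ≥7 hours.
4. Drop the word confirmed for half-life in that title and in the half-life listing of SAP 6.3.12.2, since one determination suffices.

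The cost is wording, plus at most an occasional additional SAE report. No analysis set, sample size or primary estimate changes.

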## **Hospitalization**

Hospitalization includes transfers within a hospital (e.g. from the psychiatric unit to the intensive care unit) and also includes admissions less than 24 hours. The following situations are not considered hospitalizations (although other SAE criteria may still apply):

- Outpatient procedures / ambulatory care
- Emergency department visits

Hospitalization in the absence of an adverse event occurring during the study should not be considered an SAE. This includes:

- Hospitalization due to a pre-existing condition not associated with a worsening of the pre-existing condition
- Protocol specified admission
- Pre-planned admission for a condition specified at baseline for the patient

If a patient is hospitalized due to local requirements for administration of study treatment, the hospitalization should not be considered an SAE unless another criterion/outcome for serious adverse event is fulfilled.

[figure not shown]
### **Suspected Unexpected Serious Adverse Reactions**

A Suspected Unexpected Serious Adverse Reaction (SUSAR) is an adverse reaction which is not consistent with the EU Summary of Product Characteristics (SmPC). The Sponsor will ensure that all relevant information about SUSARs involving the investigational medicinal product are reported to the relevant regulatory authorities and ethics committees in compliance with current national legislation. All SAEs are processed in the Global Safety Database held by the Sponsor's partner Bioverativ. Bioverativ is responsible for expedited reporting of SUSARs to Regulatory Authorities. Sponsor's CRO is responsible for the distribution of SUSARs to Central Ethic committees and investigators.

#### **7.5.6.1.2 Adverse event reporting period**

Any SAE experienced by the patient between the time of signature of the ICF and the safety follow-up visit is to be recorded in the CRF. In addition, any non-serious AE experienced by the patient between the time of first dose of investigational medicinal product and the safety follow-up visit is to be recorded in the CRF (Figure 3).

Furthermore, any SAE should be reported to the CRO irrespective of the time of occurrence if a causal relationship between the event and the rFVIIIFc is suspected.

**Figure 3****Adverse event reporting period**

#### 7.5.6.1.3 Eliciting and recording adverse event information

The investigator is to record all directly observed adverse events, and all adverse events spontaneously reported by the patient, in the CRF using concise medical terminology. In addition, each patient will be questioned about adverse events at each study visit following initiation of treatment. The question asked will be “Since you began taking rFVIIIFc” have you had any health problems?”

When possible and appropriate, a diagnosis rather than individual signs and symptoms shall be recorded. The investigator is responsible for obtaining sufficient information to determine seriousness, causality and outcome of each adverse event.

#### Severity assessment

The investigator will use the adjectives MILD, MODERATE, or SEVERE to describe the maximum intensity of the adverse event. For the purpose of consistency, these intensity grades are defined as follows:

MILD	Does not interfere with patient's usual function
MODERATE	Interferes to some extent with patient's usual function
SEVERE	Interferes significantly with patient's usual function

Note the distinction between the gravity (seriousness) and the intensity (severity) of an adverse event. **Severe** is a measure of intensity; thus, a **severe** reaction is not necessarily a **serious** reaction. For example, a headache may be severe in intensity, but would not be classified as serious unless it met one of the criteria for serious events listed above.

